Because XLP is an X-linked disorder, it does not affect both genders equally, but overall we expect to enroll an equal number of males and females. The cutaneous porphyrias, including the erythropoietic protoporphyrias, may be less manifest in African Americans due to protective skin pigmentation. Furthermore, the erythropoietic protoporphyrias are uncommon in Africa and in African-Americans because the low-expression allele associated with the disorder in >90% of EPP is rare in these groups. But overall, it is expected the both genders and the various ethnic groups will be represented in proportional numbers to their populations.

Inclusion of vulnerable groups: Children included as subjects of the study, since especially the erythropoietic porphyrias are manifest at birth or in early childhood. Few participants will have intellectual disabilities, as this is rarely considered a manifestation of porphyria. Pregnant women will be included in this study, since the study will not involve an intervention to place them or the fetus at increased risk, and so that we can gain a better understanding of the effects of pregnancy on the management of erythropoietic protoporphyria. As this is a longitudinal protocol and not an intervention protocol, risk to participants will be minor (as discussed in the *Potential risks* section). Information gained from this study may be valuable to this patient population.

8.B Informed consent

The mechanisms described in section 4.C will be used to recruit participants for this protocol. Any contact to recruit families will adhere to standards for ethical conduct of research and be fully HIPAA compliant. Informed consent will be obtained after the diagnosis of porphyria has been established by results of biochemical testing and/or identification of a mutation in a porphyria-related gene and the prospective subject has expressed an interest in participating in the study.

Informed consent will be obtained as follows:

1. If the prospective subject is a patient of an Investigator, and is eligible and willing to participate in the study, informed consent may be obtained in-person during a clinical visit. In a private consultation room, the investigator or delegate will explain the study and answer all questions. If the patient is willing to participate, informed consent will be obtained at this time. Consent can also be obtained over the phone. The coordinator will explain the study to the prospective subject, answer all questions, and obtain telephone consent. The consenting process will be documented by the coordinator or investigator, and the investigator will complete the eligibility form. If consent is obtained by telephone, the Informed Consent Form will be mailed, faxed, or emailed to the subject to read, sign, and return by mail, email, or fax. No study procedures will be completed until the signed consent form is received at the study site.
2. For all other prospective subjects (see 4.C. Recruitment of Subjects), once a diagnosis of erythropoietic protoporphyria is confirmed, the site-specific coordinator will contact the prospective subject by telephone. If the prospective subject or parent/guardian is interested in participating in the study, the coordinator will explain the study to the prospective subject, answer all questions, and obtain telephone consent. Eligibility status and consenting process will be documented by the coordinator or investigator who will complete the eligibility form. If consent is obtained by telephone, the Informed Consent Form will be mailed, faxed, or emailed to the subject to read, sign, and return by mail, email, or fax. When the signed consent form is received at the study site, the subject will be contacted by the study coordinator to enroll the subject into the study. It will also be explained to the participants that they are free to refuse entry into the study and free to withdraw from the study at any time without prejudice to future treatment. Written and/or oral information about the study in a language understandable by the participant will be given to all participants.

If the participant's mental age is the same as their actual age, we will follow the usual consent procedures with those 18 and over signing consent forms, and 7-17 year olds signing assent forms in addition to their

legal guardian signing consent forms. In the case of subjects who are cognitively impaired, for those 18 years old or older, informed consent will be obtained from the subject's legal guardian; for those between the ages of 7 and 17, informed consent will be obtained from the parent or legal guardian assent will be waived.

Medical Record Review – Consent will not be required for medical record review, except as may be required for obtaining outside medical records. Data collection will consist of review of medical records only. Participants identified through medical record review will be offered participation in the study.

8.C Source of material

The source of information obtained for the longitudinal study is from a patient's history, physical examination and medical records, which may include serial examinations and laboratory tests. Most of the data are from clinically indicated examinations and testing. Some data collection, such as the detailed questionnaires and the quality of life questionnaires could be considered research procedures, which although clinically useful might be more extensive than the accepted standard of care.

8.D Potential risks

This study represents not more than minimal risk, has the potential to provide a direct and long-lasting benefit for the study participants and is permissible under the provisions contained in the United States Code of Federal Regulations: 45 CFR 46.404. Most of the testing to be conducted is standard of care. The detailed data collection on clinical features and quality of life do not pose an increased risk, though the quality of life questionnaires may cause some psychological stress. There is risk of loss of confidentiality of medical and personal information, which is no more than minimal given the safeguards in place.

Participation in the study will increase the time spent during the clinical visits from approximately one hour to three hours. Visits are scheduled once yearly, or more often depending on specific clinical needs, such as frequent exacerbations or treatments.

There may be risks and discomforts associated with the blood draw: when the needle is inserted it can hurt. There is a small chance of fainting and/or bruising. Since the skin is broken, an infection at the puncture site can occur, although this is very rare. The amount of blood requested is within approved safety limits and will be modified if the subject has a medical condition that limits his/her ability to provide the requested volume of blood.

The examination of biological samples (tissue, blood and other body fluids) in general represents no direct physical harm to subjects (inflicts no physical pain or suffering). However, genetic testing carries with it the very real possibility of emotional and social risks to the subjects (the risk of harm from learning genetic information about oneself, social labeling, prejudice, unfair treatment, and potential loss of, or difficulty in, obtaining employment or insurance).

Additionally, if the subject (or parent/guardian approves, the subject's DNA and/or cells may be used in other genetic studies which may give results. However, this information will not be given to the subject until such time as the genetic test is validated as reliable, is performed in a New York State Department of Health-approved laboratory, and appropriate counseling can be provided to the subject. Additionally, no results will be provided to the subject unless he/she consents specifically for the additional testing.

Participation may result in currently unforeseeable risks to the subject.

8.E Protection against risk

The study will be conducted whenever possible within the Participant Clinical Interactions Resources of the CTSA at each of the Porphyria Consortium sites. Study visits may be conducted at alternative sites, such as a clinic facility where a porphyria patient might customarily be seen for clinical evaluation and/or treatment. The study implementers will be nursing staff/coordinators of the Centers, who will be familiar with the protocol requirements and trained in its conduct. If any unexpected and untoward event occurs during the testing procedure, such as blood drawing, emergency caregivers would be available on an immediate basis to provide necessary emergent management.

Confidentiality will be protected as required by law and as described below under *Confidentiality*.

8.F Potential benefits of the proposed research to the participants and others

Participants will have access to routine follow up that may improve their medical care and decrease risk of exacerbations, recurrences and long term complications or permit their early detection. They may also increase their understanding of their disease and their local physicians may have better access to information and advice about their management. Participants may also gain access to other studies that may involve therapy for their condition.

Genetic testing to identify the mutation in the subjects' porphyria-related gene is part of this protocol if this testing has not previously been done at an approved clinical laboratory. This testing will be performed at the Mount Sinai Genetic Testing Laboratory which is CLIA- and New York State approved to perform the molecular testing of the porphyria-related genes. The subject will be provided with the results of the molecular testing, with appropriate genetic counseling by a Board-certified genetic counselor; the results of this testing may be beneficial in that the testing is considered standard clinical information, confirms (or rules out) the diagnosis of Porphyria, and may be informative to other at-risk family members. At-risk family members, however, will not be contacted by the study team.

8.G Importance of the knowledge to be gained

This natural history study is longitudinal and should provide important information about the clinical course of the erythropoietic protoporphyrias as well as about biomarkers and correlates of outcome. The information to be learned could be useful in optimizing therapy and clinical management.

8.H Confidentiality

Patient confidentiality is protected in the fullest extent required by law and applicable local, State and Federal regulations and guidelines including HIPAA. All patient records, including case report forms, are kept in locked files accessible only to the health professionals involved in the clinical research or responsible for the patient's care, governmental agencies (e.g., FDA, NIH) and local convening authorities (e.g., IRB, D/OSMB) for the purpose of audit regarding scientific validity and/or aspects pertaining to the ethical conduct of human clinical investigation. Patient identifier data are not released without the patient's or parent's knowledge and consent or assent. Electronic databases with patient identifier data are user-access protected. Studies are conducted in the Participant Clinical Interactions Resources or clinical sites, which are also attentive to protecting confidentiality of clinical and research data. The results of the study will be shared with the participant of the study as soon as they become available.

To help protect participant privacy, a Certificate of Confidentiality has been obtained from the National Institutes of Health (NIH) for the Longitudinal Study of the Porphyrrias, which also applies to this study. With this Certificate, the researchers cannot be forced to disclose information that may identify a study participant, even by a court subpoena, in any federal, state, or local civil, criminal, administrative, legislative, or other proceedings. The researchers will use the Certificate to resist any demands for information that would identify a participant, except as explained below.

The Certificate cannot be used to resist a demand for information from personnel of the United States Government that is used for auditing or evaluation of federally funded projects or for information that must be disclosed in order to meet the requirements of the federal Food and Drug Administration (FDA).

Even with the Certificate of Confidentiality, the investigators continue to have ethical and legal obligations to report child abuse or neglect and to prevent an individual from carrying out any threats to do serious harm to themselves or others. If keeping information private would immediately put the study participant or someone else in danger, the investigators would release information to protect the participant or another person.

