 - b. Relationships between clinical and laboratory values will be evaluated in longitudinal mixed effect models. We will develop models that capture the combined frequency and severity of disease manifestations while accounting for age of onset, protoporphyria subtype (EPP and XLP), and genotype. A sample size of 150 (assuming a minimum of 3 follows ups per patient, a correlation of 0.7 among outcomes over time from the same subject, a variance of outcome equal to 1 and a compound symmetric covariance structure) yields 91% power to detect a moderate interaction ($\beta=0.4$) between time and an associated factor of interest.
 - c. A severity score based on predictive demographic and clinical characteristics will be developed
 - d. After 100 participants are enrolled, the mean score of the Hospital Anxiety and Depression Scale (HADS) will be computed and compared to the general population value. A sample size of 100 yields 90% power to detect a 20% difference in HAD-scale between the general population and our sample at the .05 significance level. The illness Perception Questionnaire and EPP/XLP-specific questionnaire will also be scored.
 - e. During this interim look at $n=100$, we will re-evaluate the estimates used in our initial power calculation that yielded a sample size of 150 and determine whether the study needs to be extended beyond this point to examine correlations of QoL scale scores with clinical severity and genotypes

Sponsors (federal, state, foundation and industry support): National institutes of Health (NIH)

1. Protocol Overview

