- 1) Participants and their family members known to the investigators who can be re-contacted and consented for inclusion, or who have previously consented for the procedures that are part of this study.
- 2) Individuals referred by the American Porphyria Foundation with known or suspected porphyria.

- 3) Individuals referred by physicians and other sources.

4.A. Inclusion criteria

There will be no exclusions based on age, race, ethnicity, or gender for this study. Inclusion criteria are based on 1) clinical features, 2) biochemical findings, as documented by laboratory reports of porphyria-specific testing performed after 1980, and 3) molecular findings documenting the identification of a mutation in a porphyria-related gene. Absolute values are preferred for diagnostic biochemical thresholds. Fold increases in comparison to an upper (or lower) limit of normal (ULN or LLN) are also acceptable, but are complicated by considerable variation between laboratories in normal limits. Equivocal biochemical measurements may require confirmation by a consortium reference laboratory. Provision is made for enrolling relatives who may not have symptoms but have biochemical or molecular documentation of a porphyria.

1. Enrollment in the Longitudinal Study of the Porphyrins (7201)
2. Willing to sign informed consent form (and provide assent if participant is a minor)
3. Biochemical findings- A marked increase in erythrocyte protoporphyrin [total erythrocyte protoporphyrin >200 ug/dL, or more than 1.5-fold increase (relative to ULN of 80 ug/dL)], with a predominance of free protoporphyrin (85-100% in EPP and 50-85% in XLP).
4. Molecular findings – one of the following:
 - a. A disease causing FECH mutation trans to the IVS3-48C>T low expression FECH allele
 - b. Two disease-causing *FECH* mutations
 - c. A gain-of-function *ALAS-2* C-terminal deletion/exon 11 mutation (in XLP)

If no mutation is found and subjects fulfill criteria 1-3 they are eligible for enrollment

We expect to enroll 150 patients with EPP/XLP.

4.B. Exclusion Criteria

We will exclude cases with elevations of porphyrins in urine, plasma or erythrocytes due to other diseases (i.e. secondary porphyrinuria or porphyrinemia), such as liver and bone marrow diseases [Gibson 2000]. We will also exclude patients with a prior diagnosis of porphyria that cannot be documented by review of existing medical records or repeat biochemical or DNA testing.

4.C. Recruitment and Enrollment of Subjects

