Table 1. CRFs Collected at Baseline and Follow-up Visits

CRFs	Visits			
	Baseline	Annual Follow-up ¹	Interim Event	Acute Symptom Phase
Completed for Longitudinal Study of the Porphyrrias (7201)				
Eligibility	X			
Sociodemographics	X	X ²		
Demographics	X			
General Medical History	X	X ²	PRN	
Concomitant Medications	X	X ²	PRN	
Family History (complete pedigree to be maintained as a source document)	X	X ²		
Baseline Disorder Specific Information: Erythropoietic Protoporphyrria	X			
Disorder Specific Information- Annual Follow-up: Erythropoietic Protoporphyrria		X		
General Physical Exam	X	X	PRN	
Porphyria Specific Lab Tests	X	X	PRN	
Local Lab Tests	X	X	PRN	
Adult PROMIS-57 Questionnaire (≥18 years old) OR Pediatric PROMIS Short Form Questionnaires- Depressive Symptoms, Anger, Anxiety, Fatigue, Pain Interference, Peer Relationships (7-17 years old)	X	X		
Completed for this Study (7207)				
7207 Eligibility	X			
EPP Specific Labs	X	X	PRN	
Hospital Anxiety and Depression Scale (HADS) (≥ 18 years old)	X	X		
EPP Specific Quality of Life Questionnaire (≥ 18 years old)	X	X		PRN
Illness Perception Questionnaire (IPQR) (≥ 18 years old)	X			
PedsQL Quality of Life Inventory (2-18 years old and parent proxy) **NOTE- a pediatric patient in 7207 does NOT need to complete the Pediatric PROMIS Short Forms	X	X		
PROMIS Pain Interference section (≥ 18 years old)				PRN
PedsQL Pediatric Pain Questionnaire (5-18 years old and parent proxy)	X	X		PRN

¹ Follow-up study visits or contacts by site coordinator will be at least on an annual basis. Symptomatic subjects will be followed as needed

² Update as appropriate

PRN= as needed

Medical record review: Local and outside medical records will be obtained, with appropriate consent, for all participants. At the time of enrollment, the participants will be asked to give permission to obtain all past and future medical records. This will provide more complete information on the clinical course of the disease, including retrospective data. To reduce unnecessary heterogeneity of the data, we will initially limit this procedure to the living participants who were diagnosed with porphyria after 1980.

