Disease Severity Score: Clinical and laboratory values assessed above will be considered potential variables to be included in an overall disease severity score. The distributions of the proposed variables to be included in the severity score will be assessed for utility to the severity score calculation. Considerations for variable utility include sufficient variability in the disease population and interrelationships with other proposed variables (if two variables are highly correlated one will be removed from the score calculation). Variables chosen to be included in the severity score will be assigned categorical ranks based on individual severity and then summed to get an overall disease severity score. The utility of the severity score will be assessed by correlating the score with clinical outcomes.

Psychosocial Impact: The following questionnaires will be administered: a) the Hospital Anxiety and Depression Scale will be used to determine the levels of anxiety and depression in these patients. These data will be scored as per the established protocol and compared to the published age-matched norms; b) the Illness Perception Questionnaire will determine the disease impact and understand how patients think and feel about their disorder. This questionnaire will determine if certain groups, such as younger adults, are more significantly impacted by this disease. The questions are scored on a Likert scale and higher scores indicate greater impairment; c) a recently validated EPP/XLP-specific questionnaire

developed in Europe will more specifically evaluate disease impact on daily functioning. After the target enrollment of n=100 is reached, we will begin the analysis.

Our primary outcome is verifying that EPP and XLP patients have higher than normal anxiety and depression. We will compare the mean Hospital Anxiety and Depression Scale (HADS) of our sample with the general population Scale (mean = 9.82, SD=5.98) (16). The null hypothesis is that there is no difference in HADS score between the general population and EPP/XLP patients.

With a sample size of 100, using a two-tailed 0.05 level one-sample t-test we will be able to detect a 20% difference in scale between the general population and our sample with 90% power.

Secondary analyses include:

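### The HADS comparison starts at 100 enrolled participants of any age, but only adults complete HADS, so the claimed 90% power for 100 scores is not delivered if any child is among them

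*Combined protocol and SAP*

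**What the plan says.** Four parts of the protocol bear on this point.

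- **Trigger.** Synopsis, Statistical Considerations, analysis plan item d: "After 100 participants are enrolled, the mean score of the Hospital Anxiety and Depression Scale (HADS) will be computed". Section 6.A (Psychosocial Impact) likewise begins the analysis once an enrolment target of 100 is reached. Neither place qualifies the 100 by age or by completed questionnaire.
- **Power.** Synopsis item d: "A sample size of 100 yields 90% power to detect a 20% difference in HAD-scale between the general population and our sample". Section 6.A: "With a sample size of 100, using a two-tailed 0.05 level one-sample t-test we will be able to detect a 20% difference in scale". The reference value in section 6.A is the "general population Scale (mean = 9.82, SD=5.98").
- **Who completes the instrument.** Section 4.E.2, Table 1, lists "Hospital Anxiety and Depression Scale (HADS) (≥ 18 years old"). Minors complete PedsQL, which plays no part in this comparison.
- **Who is enrolled.** Section 4.A: "There will be no exclusions based on age, race, ethnicity, or gender for this study". Section 8.A states that children are included, and section 2 makes the psychosocial impact on pediatric as well as adult patients a research question.

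Section 6.A gives the comparison its standing: "Our primary outcome is verifying that EPP and XLP patients have higher than normal anxiety and depression".

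**The concern.** The n in a one-sample t-test is the number of scores analysed. The trigger counts something else: participants enrolled, at any age. The two agree only if every one of the first 100 is an adult with a usable HADS form. Nothing in the plan secures that, and enrolment of children is intended.

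The plan gives no expected adult share and makes no allowance for minors or missing questionnaires. Followed as written, the test would normally run on fewer scores than its power statement requires. A non-significant result could then be reported against a stated 90% power that the analysis did not have. The same look at 100 also informs whether the study should be extended to examine quality-of-life correlations. Table 1 restricts the Illness Perception Questionnaire and the EPP-specific questionnaire to adults too, so that decision would also rest on fewer adult scores than 100.

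**Working it through.** **Inputs (section 6.A unless noted).** Reference mean 9.82; SD 5.98; difference of interest 20% of the mean; one-sample t-test, two-sided, alpha 0.05; n = 100. Planned total enrolment is 150 (section 4.A). As in the plan's own calculation, the patients' SD is taken to equal the population SD.

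**Step 1: effect size.**

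Difference = 0.20 × 9.82 = 1.964 points.
Standardised difference d = 1.964 / 5.98 = 0.328.

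**Step 2: reproduce the plan's figure.**

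Power = P(|T| > t(0.975, n − 1)), where T is noncentral t with n − 1 degrees of freedom and noncentrality d√n.

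At n = 100 the noncentrality is 0.3284 × 10 = 3.284 and power is 90.2%. The stated 90% is confirmed for 100 scores.

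**Step 3: look for slack.**

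At n = 99 power is 89.9%. Searching upward, 100 is the smallest n that reaches 90%, so the calculation has no reserve.

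**Step 4: power when some of the first 100 enrolled are minors.**

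The share of minors is not in the documents. The rows below are an assumed range and count no missing forms. The last column is the total enrolment needed to obtain 100 adult scores, 100 / (1 − share of minors), rounded up.

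| Minors among first 100 (assumed) | HADS scores | Power for a 20% difference | Difference detectable with 90% power (% of 9.82) | Enrolment needed for 100 adult scores |
|---|---|---|---|---|
| 0% | 100 | 90.2% | 1.96 points (20%) | 100 |
| 10% | 90 | 86.9% | 2.07 points (21%) | 112 |
| 20% | 80 | 82.7% | 2.19 points (22%) | 125 |
| 30% | 70 | 77.3% | 2.35 points (24%) | 143 |
| 40% | 60 | 70.6% | 2.54 points (26%) | 167 |
| 50% | 50 | 62.4% | 2.80 points (28%) | 200 |

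**Step 5: where the loss becomes material.**

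- 94 scores: 88.3%, within 2 points of 90%.
- 93 scores: 87.98%, just over 2 points below.
- 75 scores: 80.2%. 74 scores: 79.6%, the first value below 80%.

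**Step 6: whether the planned enrolment can supply 100 adult scores.**

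100 / 150 = two thirds. The planned 150 is enough if minors and missing forms together make up no more than one third of enrolment.

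**The case against.** The strongest reply is that 100 was meant as the number of adult questionnaires. Section 6.A names three instruments, all adult-only in Table 1, and then refers to an enrolment target of 100 although the study's target is 150. That could describe a separate adult psychosocial sample, in which case the power statement is right and only the wording is loose. However, synopsis item d ties the computation to enrolled participants without qualification, and no section says 100 adults or 100 completed forms. If that was the intent, the text needs the same correction.

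Other points stand in part:

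- **The size of the loss is unknown.** With few minors it is trivial, and power stays above 80% down to 75 scores.
- **The primary label is local.** It appears in the psychosocial part of section 6.A. The synopsis objectives are broader, and the total of 150 is supported by the mixed-model calculation, not by HADS.
- **More adult scores will accrue.** Enrolment continues towards 150, so the scores needed may come in anyway. But the plan specifies no repeat of the HADS test at 150.
- **The error is one of precision.** Fewer scores widen the confidence interval; they do not bias the mean or raise the type I error. No text says that a null result would be read as a 90%-power negative.

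These points limit how serious the problem may prove. They do not remove the mismatch between the two counts.

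**Conclusion.** The concern holds. The arithmetic behind the 90% is correct, but it needs 100 HADS scores, while the trigger supplies 100 enrolled participants less every minor and every missing form. The direction of the error is certain once any child is among the first 100; its size depends on an adult share that the documents do not give. Over an assumed 10% to 40% minors, power is 86.9% to 70.6%, a loss of about 3 to 20 points from the 90.2% obtained with 100 scores. At 6% minors or fewer, with complete forms, the loss is negligible. These figures keep the plan's own assumptions: an SD of 5.98, a 20% difference, and a two-sided one-sample t-test at 0.05.

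**What to change.** Preferred: in synopsis item d and in section 6.A, start the HADS analysis when 100 participants aged 18 or over have a scored baseline HADS, and state that the 100 in the power statement is that same count. The cost is a wording change in two places and a somewhat later analysis. No extra enrolment is needed if at least two thirds of the planned 150 provide an adult score.

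Alternative: keep the trigger at 100 enrolled, state the expected number of adults with scored forms, and give the power or detectable difference for that number. The cost is a less favourable stated power. Neither option adds a study procedure.
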